5.1.3.4 Permitted Concomitant Treatment

The following treatments are allowed during the study (and do not require study drug discontinuation) including, but not limited to:

- Blood transfusions and growth factor support per SOC and institutional guidelines;
- Steroid use (for indication other than prostate cancer) per SOC;

- Pain therapy per SOC and institutional guidelines;
- Palliative radiation therapy including external beam radiotherapy or systemic radionuclides (e.g., Samarium or Strontium);
- Vaccine therapy that has prior market authorization and is not intended to treat prostate cancer;
- Palliative surgical procedures to treat skeletal-related events.

5.1.4 Treatment Compliance

Study subjects should be counseled on the need to meet 100% compliance with study drug unless study drug is withheld for a toxicity. Investigator or designee should ensure that study subjects meet this goal throughout the study period. Compliance will be verified by the accounting of study drug. When study drug is administered at the research facility, it will be administered under the supervision of study personnel. If compliance is less than 80% and study drug was not withheld and there were no study drug reductions, the Investigator or designee is to counsel the subject on the importance of taking the study drug.

Compliance of the study drug will be monitored by the accounting of unused medication returned by the subject at visits. Compliance will be documented.

5.1.5 Criteria for Continuation of Treatment

This study does not set an expansion cohort, and long-term study in which this study's subject can participate is not scheduled either.

5.2 Demographics and Baseline Characteristics

5.2.1 Demographics

Demographic information will be collected at the screening visit for all subjects and will include age or date of birth, gender, race and ethnicity (as local regulations allow).

5.2.2 Medical History

Medical history will be collected at the screening visit for all subjects and includes all significant medical conditions that have occurred or are currently ongoing at time of consent. The condition, onset date and recovery date will be collected. NCI-CTCAE (version 4.03) grade will be collected for conditions that are ongoing at time of consent.

5.2.3 Diagnosis of the Target Disease, Severity, and Duration of Disease

Prostate cancer history will be collected at the screening visit and will include histological or cytological diagnosis, date of diagnosis, Gleason score and associated treatment. Date of diagnosis of metastatic disease, location of metastatic disease lesions, and all previous and/or ongoing treatment will also be documented during screening visit.

5.3 Efficacy and Pharmacokinetics Assessments

5.3.1 Efficacy Assessments

PSA response \geq 50% is defined as \geq 50% reductions in PSA level from baseline to the lowest post-baseline PSA result as determined by the central laboratory, with a consecutive assessment conducted at least 3 weeks later to confirm the PSA response.

5.3.2 Pharmacokinetics Assessments

Not applicable

5.4 Safety Assessment

5.4.1 Vital Signs

Routine vital signs, including blood pressure, pulse and temperature will be assessed at the screening visit, at every clinic visit while on study drug and at the safety follow-up visit.

5.4.2 Adverse Events

AE collection will begin at the time the informed consent form (ICF) is signed and continue until subject is determined to be ineligible for study entry, or initiation of new therapy for prostate cancer including commercial enzalutamide, or 30 days after the last dose of study drug, whichever occurs first.

See [Section 5.5 Adverse Events and Other Safety Aspects] for information regarding AE collection and data handling.

5.4.2.1 Adverse Events of Possible Hepatic Origin

See [Appendix 12.2 Liver Safety Monitoring and Assessment] for detailed information on liver abnormalities, monitoring and assessment, if the AE for a subject enrolled in a study and receiving study drug is accompanied by increases in LFTs (e.g., AST, ALT, bilirubin, etc.) or is suspected to be due to hepatic dysfunction. Subjects with AEs of hepatic origin accompanied by LFT abnormalities should be carefully monitored.

5.4.3 Laboratory Assessments

Routine laboratory samples for hematology, chemistry and PSA will be collected at the screening visit, at every clinic visit while on study drug and at the safety follow-up visit. Other laboratory assessments will be collected according to the schedule of assessments [Table 1]. Samples will be analyzed at Sponsor designated central laboratory. Analytes included are identified in [Table 2].

Hematology	Biochemistry	Other
Red blood cell count	Albumin	PSA
White blood cell count	Alkaline phosphatase	
White blood cell differential	Alanine aminotransferase	
Hemoglobin	Aspartate aminotransferase	

Table 2: Laboratory Assessments

Hematology	Biochemistry	Other
Hematocrit	Blood urea nitrogen	
Platelet count	Calcium	
	Creatinine	
	Glucose	
	Phosphorus	
	Potassium	
	Sodium	
	Total bilirubin	
	Total protein	

Clinical significance of out-of-range laboratory findings is to be determined and documented by the Investigator/Subinvestigator who is a qualified physician.

5.4.4 Physical Examination

Complete physical examination will be performed at the screening visit to assess weight, height, general appearance, skin, eyes, ears, nose, throat, neck, cardiovascular, respiratory, gastrointestinal, musculoskeletal, neurologic status, mental status, lymphatic and genitourinary systems.

A brief physical examination with weight will be performed at day 1, all subsequent clinic visits while on study drug and at the safety follow-up visit. New or worsening clinically significant findings on physical examination will be recorded as AEs if they meet the criteria in [Section 5.5.1 Definition of Adverse Events].

5.5 Adverse Events and Other Safety Aspects

5.5.1 Definition of Adverse Events

An AE is any untoward medical occurrence in a subject, temporally associated with the use of a medicinal product, whether or not considered related to the medicinal product. An AE can therefore be any unfavorable and unintended sign (including an abnormal laboratory finding), symptom, or disease (new or exacerbated) temporally associated with the use of a medicinal product.

In order to identify any events that may be associated with study procedures and could lead to a change in the conduct of the study, Astellas collects AEs even if the subject has not received study drug treatment. AE collection begins after the signing of the informed consent and will be collected until subject is determined to be ineligible for study entry, or initiation of new therapy for prostate cancer including commercial enzalutamide, or 30 days after the last dose of study drug, whichever occurs first.

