Adverse events (AEs) will be coded using the Medical Dictionary for Regulatory Activities (MedDRA). The number and percentage of subjects with treatment-emergent AEs, serious AEs (SAEs), AEs leading to withdrawal of treatment, and AEs possibly related to the study drug will be calculated. Changes in laboratory parameters, vital signs, and weight over time will be tabulated. **Efficacy:**

The PSA response rate will be summarized by time point.

Pharmacokinetics:

Not applicable

Pharmacodynamics:

Not applicable

Interim analyses:

An interim assessment will be conducted at 6 month from first subject enrollment, with respect to safety. The report will be submitted to the health authority.

V. FLOW CHART AND SCHEDULE OF ASSESSMENTS

Flow Chart

Study Day	Screening Visit	1	29	57	85	169 & every subsequent 84 days	Safety Follow-up	Unscheduled
Study Week	-4 to -1 (28 Days)	1	5	9	13	25	30 Days after Last Dose§	Visit†
Window (Days)			± 7	± 7	± 7	± 7	± 7	NA
Informed Consent	Х							
Medical History	Х							
Inclusion/Exclusion Criteria	Х	Х						
IRT		Х						
Vital Signs	Х	Х	Х	Х	Х	Х	Х	Х
Physical Examination including Weight¶	Х	Х	Х	Х	Х	Х	Х	Х
Height	Х							
Clinical Labs ‡	Х	Х	Х	Х	Х	Х	Х	Х
PSA	Х	Х	Х	Х	X	Х	Х	
ECOG Performance Status	Х							
Adverse Events§§	Х	Х	Х	X	X	Х	Х	Х
Previous and Concomitant Medications	X	Х	Х	Х	Х	X	Х	Х
Study Drug Dispensing		Х	Х	Х	X	Х		
Study Drug Treatment		Х	Х	X	Х	Х		

Table 1: Schedule of Assessments

ECOG: Eastern Cooperative Oncology Group; IRT: Interactive Response Technology; NA: not applicable; PSA: prostate-specific antigen

- [†] Unscheduled visits may be performed at any time during the study whenever necessary to assess for or follow-up on adverse events at the subject's request or if deemed necessary by the Investigator. Procedures and assessments are to be performed as clinically indicated.
- § Or prior to initiation of an investigational agent or new therapy for prostate cancer, whichever occurs first.
- A brief physical examination is required at each visit, with the exception of the screening visit during which a complete physical examination will be completed.
- ‡ Laboratory assessments include serum chemistries and hematology.

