- §§ Adverse events will be collected from the time the subject signs the consent form until the end of the safety reporting period (or until screen failure). The safety reporting period ends at the time of the safety follow-up visit, 30 days after last dose of study drug or initiation of an investigational agent or new therapy for prostate cancer.

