1.2.2 Clinical Data

As of the data cutoff date of 28 February 2016, over 5500 subjects with prostate cancer, over 400 women with breast cancer, and over 300 subjects with no known cancer including healthy male subjects and subjects with hepatic impairment have received at least 1 dose of enzalutamide in completed and ongoing clinical studies (not including the expanded access program or 2 compassionate use programs). Enzalutamide was approved by DCGI for treatment of adult men with metastatic castration-resistant prostate cancer whose disease has progressed on or after docetaxel therapy on 28 April 2016 and commercially available on July 2016. As of 26 March 2017, 174 patients have received the treatment.

The pharmacokinetics and metabolism of enzalutamide have been evaluated in more than 2500 subjects with prostate cancer and in more than 200 healthy male subjects and subjects with mild, moderate, or severe hepatic impairment. Individual daily doses have ranged from 30 to 600 mg.

The pharmacokinetics of a single oral 160 mg dose of enzalutamide were examined in subjects with baseline mild, moderate or severe hepatic impairment (Child-Pugh Class A, B, and C, respectively) and in matched control subjects with normal hepatic function (Study 9785-CL-0009 and Study 9785-CL-0404). Mild, moderate or severe hepatic impairment did not have a clinically relevant effect on the composite AUC of enzalutamide plus *N*-desmethyl enzalutamide. Therefore, the results indicate that no starting dose adjustment is necessary for subjects with baseline mild, moderate or severe hepatic impairment.

After oral administration to subjects with CRPC, the median time to reach maximum enzalutamide plasma concentrations was 1 hour, and the mean terminal half-life was 5.8 days. Enzalutamide steady state was achieved by day 28, and the accumulation ratio was 8.3-fold. At steady state, enzalutamide showed approximately dose-proportional pharmacokinetics over the range of 30 to 360 mg/day. Steady-state plasma levels of the active metabolite are similar to those of enzalutamide.

A mass balance and biotransformation study in healthy male volunteers showed that enzalutamide is primarily eliminated by hepatic metabolism. A food-effect study showed that food does not have a clinically relevant effect on the AUC of enzalutamide or *N*-desmethyl enzalutamide; therefore, enzalutamide can be taken with or without food.

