2.2 Study Design and Dose Rationale

2.2.1 Study Design

This study is a multicenter Phase 4, open-label, single-arm, safety and efficacy study of enzalutamide (160 mg/day) in patients with progressive mCRPC who have previously been treated with docetaxel-based chemotherapy. Approximately 50 patients will be enrolled and treated with enzalutamide 160 mg once daily until study discontinuation criteria is met.

Safety and tolerability will be assessed by the collection of adverse events, vital signs, physical examinations and safety laboratory evaluations.

PSA will be collected for assessment of prostate cancer status on Screening Visit, Days 1, 29, 57, 85, 169, every subsequent 84 days and Safety Follow-up Visit.

Subjects will have a safety follow-up visit 30 days after their last dose of study drug or prior to initiation of another investigational agent or new therapy including commercial enzalutamide for prostate cancer, whichever occurs first.

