6 DISCONTINUATION

6.1 **Discontinuation of Individual Subject(s)**

The subject is free to withdraw from the study treatment and/or study for any reason and at any time without giving reason for doing so and without penalty or prejudice. The Investigator is also free to terminate a subject's involvement in the study at any time if the subject's clinical condition warrants it.

Discontinuation Criteria from Study Drug Treatment for Individual Subjects:

- Any AE that is intolerable to the subject which cannot be ameliorated by the use of adequate medical intervention and/or dose reduction or that in the opinion of the Investigator would lead to undue risk to the subject if dosing is continued.
- Subject who experiences a seizure or any condition that significantly predisposes the subject to seizure such as brain metastasis or clinically evident stroke.
- Subject who experiences a confirmed event of PRES by brain imaging, preferably by MRI.
- Subject initiates an investigational agent or new therapy for prostate cancer.
- Subject who has evidence of radiological disease progression and/or PSA progression as confirmed by the Investigator and is no longer deriving clinical benefit. Imaging test can be done at the discretion of the investigator and are not part of the study.
- Subject has discontinued ADT (GnRH agonist/antagonist) and has a testosterone value in the noncastrate range (> 50 ng/dL).
- Subject who is, in the opinion of the Investigator or the Medical Monitor, non-compliant with the protocol requirements.
- Subject is lost to follow-up despite reasonable efforts by the Investigator to locate the subject.
- Subject withdraws consent for the study.

Subject will be discontinued from the 30 day study follow-up (Safety or Long-term Follow-up) if any of the following occur:

- Subject is lost to follow-up despite reasonable efforts by the Investigator to locate the subject.
- Subject withdraws consent for further follow-up.
- Death.
- Study termination by the Sponsor.

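### Routine AE and SAE collection closes when a subject starts new prostate cancer therapy or commercial enzalutamide, even within 30 days of last dose, and the sections word this trigger differently

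*Protocol*

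**What the plan says.** Protocol 5.4.2 and 5.5.1 collect AEs from consent until the earliest of three events: the subject is found ineligible, "initiation of new therapy for prostate cancer including commercial enzalutamide", or the 30th day after last dose.

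Protocol 5.5.5 continues SAE reporting to the safety follow-up visit. By 2.2.1, repeated in SAP 3.2, that visit falls 30 days after last dose or "prior to initiation of another investigational agent or new therapy including commercial enzalutamide for prostate cancer, whichever occurs first". The Table 1 footnote on the visit gives a shorter trigger: "Or prior to initiation of an investigational agent or new therapy for prostate cancer, whichever occurs first". The Table 1 footnote on AEs ends the safety reporting period at the visit, described as "30 days after last dose of study drug or initiation of an investigational agent or new therapy for prostate cancer".

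Protocol 6.1 lists as a reason to stop study drug: "Subject initiates an investigational agent or new therapy for prostate cancer". Its separate list of reasons for leaving the 30-day follow-up contains only loss to follow-up, withdrawn consent, death and termination by the sponsor.

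Once collection has closed, 5.5.6 requires prompt notification of an (S)AE, including death, if the investigator learns of it and sees a reasonable possibility that study drug or participation caused it. Existing AEs are followed to resolution. SAP 6.2 defines a TEAE as any AE after dosing starts and sets no end date.

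**The concern.** Safety and tolerability is the primary objective, and 5.5.1 defines an AE without regard to relatedness. After a switch within the 30 days, what remains reportable is narrower than that definition: the event must reach the investigator and must be judged related. Table 1 schedules no contact after the visit that precedes the switch. Section 5.5.3 asks for a causality answer of no when information is too limited to judge, which is the likely position once contact has ended. Serious events and deaths in early switchers can then be absent from the TEAE and death tables without anyone having broken the protocol.

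Commercial enzalutamide is the hardest case to justify. Closing collection at a different agent avoids crediting its toxicity to study drug. A subject who moves to commercial supply keeps taking the same drug, so that reason does not apply. The move is plausible: 1.2.2 says the drug has been on the Indian market since July 2016, and 5.1.5 says no long-term study follows.

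Because the trigger is worded in several ways, two sites could close collection on different dates for the same history.

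**Working it through.** The plan states no figure to reproduce; the sample size of 50 is not based on a power calculation (Protocol 7.1). The check is mainly a comparison of wording.

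| Place | What it governs | Commercial enzalutamide named | Investigational agent named |
|---|---|---|---|
| Protocol 5.4.2, 5.5.1 | End of AE collection | Yes | No |
| Protocol 2.2.1, SAP 3.2 | Timing of follow-up visit | Yes | Yes |
| Table 1, visit footnote | Timing of follow-up visit | No | Yes |
| Table 1, AE footnote | End of safety reporting period | No | Yes |
| Protocol 6.1 | Stopping study drug | No | Yes |
| Protocol 6.1 | Leaving 30-day follow-up | New therapy is not a listed reason | New therapy is not a listed reason |
| Protocol 5.5.5 | End of SAE reporting | Tied to the visit | Tied to the visit |
| SAP 6.2 | TEAE | No end date | No end date |

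Two smaller differences follow. The Table 1 AE footnote does not say that the earlier of its two dates applies. Section 5.5.5 ends with a visit that has a window of ±7 days, while 5.4.2 and 5.5.1 use a fixed 30 days.

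**Exposure when collection closes (switch to a different agent).** Protocol 1.2.2 states that "the mean terminal half-life was 5.8 days". The fraction remaining after t days is 0.5^(t/5.8):
- day 1: 0.887
- day 7: 0.433
- day 14: 0.188
- day 30: 0.028

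Thirty days is 30/5.8 = 5.2 half-lives, so the nominal window covers most of the washout and an early switch does not. This treats the decline as first order and covers parent drug only; 1.2.2 gives no half-life for the active metabolite. With commercial enzalutamide there is no washout.

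**Days closed per switcher.** This is 30 − gap: 29 days for a gap of 1 day, 23 for 7 days and 16 for 14 days.

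**Scale across the study (illustration only).** Fifty subjects followed for 30 days give 50 × 30 = 1500 person-days. Both the share who switch and the gap are assumptions.
- Low: 10% switch at 14 days, 5 × 16 = 80 person-days, or 5%.
- High: 42% switch at 1 day, 21 × 29 = 609 person-days, or 41%.

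If each switcher had an assumed 2% to 10% chance of a serious event in the closed days, the chance of at least one is 1 − (1 − r)^k. That is 10% to 41% for k = 5 and 35% to 89% for k = 21. Some of these events would still be reported under 5.5.6.

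**Weight of one subject.** 1/50 = 2 percentage points.

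**The case against.** The strongest defence is that ending collection at a new therapy keeps confounded events out of a single-arm, descriptive study in which no comparison between arms can be biased. Section 5.5.6 still brings in related (S)AEs and deaths, ongoing AEs are followed, and the open-ended TEAE definition would admit late reports. The SAP overview (7.5.1.1) counts deaths separately from TEAEs leading to death.

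Much of this stands. A reader might infer that all SAEs and deaths in switchers are lost; 5.5.6 rules that out. The defence does not cover events judged unrelated or never learned of, and its confounding argument fails for commercial enzalutamide. Nor do the documents say whether reports under 5.5.6 enter the clinical database.

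Four other strong readings are tempting and not supported:
- That permitted palliative treatment closes collection while study drug continues. Section 5.1.3.4 allows "Palliative radiation therapy including external beam radiotherapy or systemic radionuclides" without stopping study drug, whereas 6.1 makes new therapy a reason to stop it. Read together, the permitted treatments are not new therapy.
- That switchers have no post-treatment safety data. A subject who stops for another reason and then plans a switch has the visit first and keeps the interval up to the switch. Only a subject who starts new therapy while still on study drug cannot meet the visit rule.
- That disposition tables mix users of commercial drug with treatment failures. Section 2.2.1 governs visit timing; SAP 7.2.1 tabulates by primary reason, and the CRF categories are not in the documents.
- That the number affected can be computed from the 42.0% with subsequent therapy in the cited post-docetaxel phase 3 study (Protocol 1.4). That figure carries no time limit, and no document gives the share within 30 days of last dose.

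**Conclusion.** The point holds in a limited form. Routine AE and SAE collection can close before day 30 after last dose. From then on, only events that are known to the investigator and judged related remain reportable. The trigger wording is inconsistent across 5.4.2/5.5.1, 2.2.1, Table 1 and 6.1. The 30-day follow-up in 6.1 does not end at new therapy, although AE collection does, and the SAP sets no TEAE end date.

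For an affected subject the gap is material, because collection can close while exposure is substantial or, with commercial drug, unbroken. For the study as a whole the size is unknown: the person-day and probability ranges rest on assumed switching shares, gaps and event rates, and are not estimates. The result is possible under-counting of serious and fatal events in the primary safety summaries. It is not a demonstrated loss, and it does not invalidate the design. It should be corrected because the remedy is cheap and bears on the primary endpoint.

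**What to change.** 1. Use one trigger wording in Protocol 2.2.1, 5.4.2, 5.5.1, 5.5.5 and both Table 1 footnotes, with SAP 3.2 to match, stating how commercial enzalutamide and investigational agents are treated. Reconcile 6.1 with it; this review takes no position on the treatment-stopping criterion itself.
2. Collect at least SAEs and deaths through 30 days after the last dose of study drug whatever therapy follows, including commercial enzalutamide, regardless of causality.
3. Record the start date of the new therapy. Protocol 5.1.3 documents concomitant medication only up to the final follow-up visit, which is meant to precede the switch, so the date is not assured at present.
4. In the SAP, give TEAEs an end date, flag events that start after a switch, and show TEAE summaries with and without them. State whether reports received under 5.5.6 enter these tables.

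The cost is protocol wording, one eCRF date, one flag in the AE dataset and a brief contact with each switcher. Some flagged events will be due to the new therapy; the paired summaries keep that visible. If subject follow-up is already over, item 4 can still be settled before database hard lock as far as the recorded dates allow, and the study report should state the cut-off that applied.
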